## 1 Background

Despite the good results obtained with coronary arteries revascularization after primary percutaneous coronary interventions (PCI) in ST-elevation myocardial infarction (STEMI) patients, a significant portion of patients may have a poor outcome due to the presence of microcirculation coronary damage.

Microcirculation evaluation is now potentially possible through the index of microcirculatory resistance (IMR), which was first evaluated in animal models and in stable patients.

IMR measurement, which expresses the micro-vascular function, can be done through a pressure sensor / thermistor-tipped guidewire.

The potential advantages of IMR over current methods (Thrombolysis in myocardial infarction Myocardial Perfusion Grade (TMPG), coronary flow reserve (CFR), resolution of the sum of ST-segment elevation (ST-resolution), corrected Thrombolysis in myocardial Frame Count (cTFC), Myocardial Contrast Echo Score Index (MCESI)) to evaluate the microcirculation are: relative ease of use and interpretation, quantitative nature, independence of the epicardial vessels and reproducibility.

The relative ease and measurement reproducibility of IMR shows lot of advantages if compared with the microcirculation assessment by traditional methods.

IMR obtained by this technique was measured in STEMI patients after primary PCI and compared to traditional methods to assess the microvasculature.

Compared to standard measures, IMR appears to be a better predictor of microvascular damage after STEMI, both acutely and in short term follow-up.

IMR is a reliable early on-site determinant of myocardial viability and LV recovery after stenting for acute myocardial infarction (AMI). However, the correlation between short and mid-term outcomes and IMR values measured during treatment with PCI in STEMI patients is currently not yet well defined.

The purpose of this study is to detect any correlation between IMR and the short and medium term outcomes, defined as cardiovascular death, re-Myocardial Infarct (MI), re-hospitalization for Heart Failure (HF), resuscitation or Implantable Cardioverter Defibrillator (ICD) appropriate shock, in this population.

## 2 Study Purpose

### 2.1 Objectives

#### Primary Objective

To assess whether the IMR can be considered a prognostic predictor for the occurrence of events (as hereinafter further defined) at one year of follow up after primary PCI in STEMI patients.

#### Secondary Objectives

Evaluation of:

- A better cut-off of IMR for the prognosis of study patients
- New CHF during index hospitalization

- Left Ventricular remodeling
- Incidence of new revascularization
- Incidence of stent thrombosis
- ST Resolution or residual ST elevation
- Possible predictors of patient outcomes

## 2.2 *Endpoints*

### 2.2.1 Primary Endpoints

Composite of: cardiovascular death\*, re-myocardial infarct, re-hospitalization for heart failure (HF, CHF), resuscitation or ICD appropriate shock, at 1 year.

\* Timing for mortality evaluation: once culprit lesion has been evaluated through IMR

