### **3.2.1 Procedures**

Primary PCI is performed as soon as possible, following the center clinical practice, to treat the culprit lesion. Drug Eluting Stent (DES) of choice in the center and required by the lesion anatomy will be used following the usual clinical practice. FFR and IMR will be measured at the end of the procedure.

Staged procedure to treat the non-culprit lesion will be performed before hospital discharge as per normal clinical practice of the center. FFR and IMR will be measured and lesion will be treated only if FFR will show functional stenosis. Distal lesion that can't be crossed with the guidewire will be treated as per clinical practice. Drug Eluting Stent (DES) of choice in the center and required by the lesion anatomy will be used following the normal clinical practice in each center. FFR and IMR will be measured at the end of the procedure. An ECG will be assessed approximately 90 minutes after primary PCI procedure. A TTE (Echo) will be performed before the patient discharge.

Medical therapy during the procedure and at the hospital discharge will be driven by usual clinical practice, guidelines and standard of care recommendations.

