### **3.5.3 Procedure for assessing, recording and reporting Adverse Events, Adverse Device Effects, Serious Adverse Events and Serious Adverse Device effects**

Safety surveillance and reporting will be done for all patients enrolled in this study.

Safety surveillance within this clinical investigation and safety reporting, both performed by the investigator, starts as soon as the patient is enrolled in this clinical investigation (date of signature of the informed consent). The safety surveillance and the safety reporting will continue until the last follow-up visit has been performed or the patient is deceased or the patient/investigator concludes his participation into the clinical investigation.

NOTE: If an adverse event is documented at the patient's last follow up visit, both the notification and follow-up information on the AE CRF are to be provided to the sponsor.

- All serious Adverse Events and all Adverse Device Effects (serious or non-serious) are to be documented and reported to the sponsor maximum 3 calendar days after becoming aware of the event.
- Non-serious adverse events documentation and reporting are limited to cardiovascular and neurovascular events and to events endpoints related.

Should an AE occur, record AE information in the hospital records, document the information into the adverse event form as soon as possible. By completing the form, the sponsor will be notified. Refer to Table 1: Data Collection and Appendix F for Data Collection Method. In case of EDC failure, notify Sponsor via Fax ([contact]) or via [[contact]](mailto:[contact]).

Sponsor will be responsible for ensuring the assessment of immediate AE 'reportability' or 'non-reportability' to the competent authorities. All the reported AEs will be documented and reported in a periodic report.

Additional information may be requested, when required, by the sponsor in order to support the reporting of AEs to regulatory authorities and to support AE analysis. The investigator must notify the EC, if appropriate, in accordance with national and local laws and regulations, of the AEs reported to the sponsor.

In case of disagreement between sponsor and investigator in the AE assessment, then both assessments will be reported.

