## 4 Scientific Soundness

### 4.1 Sample Size

Study aim is to assess/explore, in a cohort of STEMI patients at 1 year of follow-up from primary PCI, if categorization of IMR based on the median value can be considered a predictive / prognostic for the occurrence of cardiovascular events such as death, re-MI, re-hospitalization for HF, resuscitation or appropriate ICD shocks.

It is believed, based on the events reported in similar cohort of patients , that the expected events at one year should be of 12-16%.

The present study aims to demonstrate that the incidence of events is significantly different in the two subpopulations of patients with IMR upper and lower of the value of 32, found by Fearon et al.; other authors found the median value as event predictor.

Based on these assumptions, hypothesizing an incidence of events/year by 7% in the group of patients with IMR values below its median and 21% in the group with higher values of IMR, with an alpha error = 0.05, a power of 85% and applying the two tails Chi-square test, it is estimated that 218 patients are needed.

Providing a dropout rate of 10%, the number of patients who must be enrolled will be 242.

It is assumed that the participant centers will be up to 20. Based on number of cases in previous year evaluation, enrollment mean rate is assumed to be approximately 6-10 patients/year/center.

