### **Definition of Heart Failure**

The clinical outcome of Heart Failure will include re-hospitalization for CHF and new or worsening CHF occurring during the hospitalization. New CHF during the hospitalization must have an onset or persist >24h after hospital admission. Worsening of CHF must occur or persist >24h after hospital admission.

Congestive heart failure is defined on the basis of the physician's decision to treat CHF with an IV diuretic, IV inotropic agent, or IV vasodilator, and at least 1 of the following:

- Presence of pulmonary edema or pulmonary vascular congestion on chest radiograph believed to be of cardiac cause.
- Rales >1/3 up the lung fields believed to be due to CHF.
- Pulmonary capillary wedge pressure or left ventricular end diastolic pressure >18 mm Hg.
- Dyspnea, with documented  $pO_2 <80$  mm Hg on room air or oxygen saturation <90% on room air, without significant lung disease.

Rehospitalization for CHF is readmission to an acute care facility primarily for the treatment of CHF and includes treatment of CHF with an IV diuretic, IV inotropic agent, or IV vasodilator.

Readmission also includes patients who are treated and under observation for at least 12 hours at a medical care facility but are not formally admitted as inpatients.

Patients readmitted primarily for treatment of a recurrent ischemic episode will not be considered to have met the rehospitalization for CHF criteria.

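### Does the plan need a written start time for the non-fatal primary events, and a rule for in-hospital heart failure?

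*Combined protocol and SAP*

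**What the plan says.** Section 2.2.1 defines the primary endpoint as a composite of cardiovascular death, re-infarction and "re-hospitalization for heart failure (HF, CHF), resuscitation or ICD appropriate shock, at 1 year". An asterisk on cardiovascular death leads to the footnote "Timing for mortality evaluation: once culprit lesion has been evaluated through IMR". The other components have a stated end but no start of their own.

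The general time frame appears in two places. The primary objective (Section 2.1) concerns events "at one year of follow up after primary PCI in STEMI patients". Section 4.1 describes the aim "in a cohort of STEMI patients at 1 year of follow-up from primary PCI". For the culprit lesion, Section 3.2.1 says "FFR and IMR will be measured at the end of the procedure". Safety reporting under Section 3.5.3 begins earlier, on the date the consent form is signed.

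On heart failure, the Appendix A definition opens with "The clinical outcome of Heart Failure will include re-hospitalization for CHF and new or worsening CHF occurring during the hospitalization", and further down states "Rehospitalization for CHF is readmission to an acute care facility primarily for the treatment of CHF". Section 2.2.2 lists new CHF during the index admission among the secondary endpoints. Worsening CHF during that admission appears only in Appendix A.

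**The concern.** The primary question is whether IMR predicts later events, and an event that precedes the reading cannot be predicted by it. The plan acts on this for death and is silent for the rest, which invites the reading that the other components start somewhere else. Because reporting opens at consent and IMR is read at the end of the PCI, the whole procedure lies inside event capture but before the predictor is known. If resuscitations or re-infarctions from that window entered the composite and were unrelated to IMR, they would dilute the contrast between the two IMR groups.

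The opening sentence of the Appendix A definition raises a second doubt. It could be taken to bring in-hospital heart failure into the primary composite. That could matter more. If such failure were unrelated to IMR and occurred in an assumed 5% or 10% of patients, exact power would fall from 0.870 to 0.732 or 0.615. If it tracked IMR, the association would look stronger. With the rule unwritten, the choice could in principle be made after results are seen.

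**Working it through.** **Step 1. Reproduce the plan's figure.** Inputs from Section 4.1: 7% and 21%, two-sided alpha 0.05, power 85%, chi-square test. The median split implies equal groups. With pooled variance and no continuity correction, and p̄ = (0.07 + 0.21)/2 = 0.14:

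n = [1.960 × √(2 × 0.14 × 0.86) + 1.036 × √(0.07 × 0.93 + 0.21 × 0.79)]² / 0.14²

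= [1.960 × 0.4907 + 1.036 × 0.4806]² / 0.0196 = 108.7, so 109 per group and 218 in total, as stated. Dividing by 0.90 for dropout gives 242.2, against the stated 242.

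Power at 109 per group is 0.851 by the same normal approximation. Exact binomial enumeration of the uncorrected chi-square test gives 0.870. The exact figure is the baseline below.

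**Step 2. Which components can fall before IMR?** Section 3.2 places consent after the diagnostic angiogram, so the window from consent to the IMR reading is essentially the PCI itself.

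- Readmission for heart failure cannot occur in it.
- An ICD shock needs a device already in place.
- A re-infarction is hard to separate from the infarction under treatment.
- Resuscitation during the procedure is the realistic case. Section 2.3.2 narrows it by excluding patients with haemodynamic instability that drugs cannot control or who need a balloon pump.

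**Step 3. Size of the dilution.** The documents give no rate of pre-IMR events, so the rate h is an assumption. Suppose every such event is wrongly counted, occurs equally in both groups, and is independent of later events. Each group's rate becomes 1 − (1 − p)(1 − h).

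| h | Patients of 218 | Low IMR | High IMR | Exact power |
|---|---|---|---|---|
| 0 | 0 | 7.0% | 21.0% | 0.870 |
| 0.5% | 1.1 | 7.5% | 21.4% | 0.856 |
| 1% | 2.2 | 7.9% | 21.8% | 0.842 |
| 2% | 4.4 | 8.9% | 22.6% | 0.814 |

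For example, at h = 1% the low group is 1 − 0.93 × 0.99 = 0.0793 and the high group is 1 − 0.79 × 0.99 = 0.2179. The difference is 13.9 points instead of 14.0. The normal approximation shows a similar fall, from 0.851 to 0.825 at 1%.

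**Step 4. Where does in-hospital heart failure go?** Set side by side:

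- Section 2.2.1 (primary): re-hospitalization for heart failure. Sections 1, 2.4 and 4.1 use the same term.
- Section 2.2.2 (secondary): new CHF in the index admission. Section 2.1 lists the same item as a secondary objective.
- Appendix A: re-hospitalization is a readmission, which an event in the index stay cannot be.

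Section 2.2 assigns endpoints, and Appendix A defines the terms used there. Read together, they keep in-hospital heart failure out of the primary composite. The power figures of 0.732 and 0.615 therefore describe a composite that the plan does not specify. The only term without an endpoint is worsening CHF during the index stay.

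**The case for a change.** The best case for a change is that the sponsor saw the time-zero question and settled it for one component, when one sentence would have settled it for all. The wording elsewhere is not airtight. Counting from primary PCI, as in Section 4.1, can be read to include the procedure. Table 1 records adverse events in the PCI column, and Section 3.5.2 names myocardial infarction and serious arrhythmia as possible complications of catheterization. Appendix A has no definition of re-infarction or resuscitation that would screen out procedural events. The Kaplan-Meier and Cox analyses in Section 4.2 need one origin, and none is stated.

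The textual point stands: no sentence expressly excludes a non-fatal event before IMR. The consequence does not follow. Section 3.5.3 governs safety reporting, so recording an event there does not make it a primary endpoint. The objective's wording, after primary PCI, points to exclusion, and the death footnote shows the intent. For the time-to-event analyses, the PCI and the culprit IMR reading belong to the same procedure, so the choice between them hardly alters follow-up measured over a year.

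The omission of worsening CHF from Sections 2.1 and 2.2.2 is also real, but it concerns the wording of a secondary endpoint.

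**Conclusion.** This is missing detail that analysts would fill sensibly, and no change to the plan is needed. Followed as written, the plan counts primary events after the primary PCI, at whose end IMR is read, and counts only readmissions for heart failure.

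Even if the gap were filled badly, an assumed 0.5% to 1% of patients with a pre-IMR event would leave exact power at 86% or 84%, close to the planned 85%; at 2% it would be 81%. The figures of 218 and 242 are unaffected. These results assume pre-IMR events unrelated to IMR and independent of later ones, with 7% and 21% describing the events after IMR. The documents do not supply the pre-IMR rates, so they show scale and are not forecasts. The larger effects require in-hospital heart failure to count as primary, which Section 2.2 and the readmission definition in Appendix A do not support.

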### 2.2.2 Secondary Endpoints

- Evaluation of a better cut-off of IMR index based on primary endpoint events
- New CHF during index hospitalization
- Left Ventricular (LV) remodeling @ 1y (improvement of EF%, LVESV, LVEDV, LVEDD, LVESD, 16 segments WMSI and mitral insufficiency, assessed by TTE)
- Need for new revascularization @ 1y (revascularization yes/no)
- Stent thrombosis @ 1y (thrombosis yes/no)
- ST resolution or residual ST elevation post PCI (Electrocardiographic ST-segment elevation in two or more contiguous electrocardiogram (ECG) leads)
- Evaluation of possible events predictors including but not limited to age, sex, infarct area, Killip risk, number of PCI

## 2.3 *Patient Selection Criteria*

A patient who meets all the inclusion criteria and does not meet any of the exclusion criteria is eligible to participate in the investigation. A patient is enrolled in the investigation only when s/he has provided written informed consent. Once enrolled, a patient is expected to comply with the scheduled visits and required activities according to the protocol.

### 2.3.1 Inclusion Criteria

Patients meeting all the inclusion criteria could be considered for inclusion in the study:

- Patient of legal age in hosting country able and willing to provide informed consent form
- Hospital admission either within 12 h of symptom onset or between 12 and 24 h after onset with evidence of continuing ischemia
- Electrocardiographic ST-segment elevation  $\geq 1$  mm in two or more contiguous ECG leads, or with a left bundle-branch block (LBBB)
- Multivessel diseased patients with lesions in the proximal 2/3 part of the vessels
- Culprit Lesion EB identified during evaluation of basal angiography
- Presence of at least one non-culprit lesion  $>50\%$  EB detected in the basal angiography and eligible for PCI for which the operators decision is to perform a staged pre-discharge angioplasty procedure

### 2.3.2 Exclusion Criteria

Patients will be excluded from the study if they meet any of the following criteria:

- Patients who cannot give informed consent
- A life expectancy of less than 1 year
- Patients who are pregnant or nursing
- Contra-indication to angiography
- Allergy/intolerance to Adenosine
- Contra-indication/Allergy/Intolerance to contrast media or to medical therapy foreseen for PCI
- Documented allergy to Adenosine diphosphate (ADP) inhibitors (aspirin and clopidogrel)
- New infarct on the same area of a previous infarct
- Critical non treatable Lesion EB>70% downstream of the culprit lesion
- Absence of non-culprit lesion/s
- Patient with hemodynamic instability not controllable with medical therapy and/or need intra aortic balloon pump implantation (IABP)
- Prior Coronary Artery Bypass Graft (CABG) or indication for CABG
- Patients with Left Main (LM) coronary artery disease requiring revascularization

[figure not shown]
### 2.4 Study Design

This is a prospective, multicenter study designed to evaluate IMR ability to predict events occurrence, defined as Cardiovascular death, re-MI, re-hospitalization for HF, resuscitation or ICD appropriate shock, during a 1 year follow-up period.

[figure not shown]
Patients will be enrolled in the study at hospital admission after the pathology assessment has been done. All participants will have the culprit lesion treated following clinical practice and guidelines ; Fractional Flow Reserve (FFR) and IMR will be measured after the primary PCI procedure to evaluate treatment success and myocardial viability. Non-culprit lesions will be functionally evaluated through FFR index and will be treated if FFR will show functional stenosis . FFR and IMR will be measured to evaluate treatment success and myocardial viability. Patients will be followed-up at 1m, 6m and 1y periods.

Device used to assess FFR and IMR is already in use in clinical practice at participating centres. The wire is used following indication for use (IFU), guidelines and clinical practice in the selected centers.

**Fig. 1: Study Flow-Chart**

**Fig. 2: Patient Procedure Flow**

**Table 1: Data Collection**

	Enrollment	PCI Procedures	90 min post PCI	Pre Discharge	1m f-up	6m f-up (phone)	1y f-up
Patient Eligibility	✓						
Informed consent	✓						
Demographic data	✓						
Medical History	✓						
Risk and Functional Classifications	✓	✓		✓	✓	✓	✓
Medications	✓	✓		✓	✓	✓	✓
Enzymes	✓@	✓@		✓@	✓+		✓+
Cholesterol/ Triglycerides	✓¢	✓¢		✓¢	✓+		✓+
ECG	✓	✓#	✓*	✓			
TTE (echo)				✓			✓
Procedure Data		✓					
IMR-FFR		✓					
F-up clinical status					✓	✓	✓
Adverse Events		✓§	✓§	✓§	✓§	✓§	✓§

#: post procedures

\*: only for primary PCI (cont.)

§: if applicable

+: if available per center practice

ç: at least once during the patient hospitalization, values as available per local laboratory and center practice

@: at least twice during the patient hospitalization, strongly recommended at baseline and post-primary PCI visits, values as available per local laboratory and center practice

## 2.5 Devices Used

### 2.5.1 Device used to assess IMR and FFR

Index of Microcirculatory Resistance (IMR) and Fractional Flow Reserve (FFR) index will be assessed by St Jude Medical PressureWire® guidewire.

PressureWire® is indicated to direct a catheter through a blood vessel and to measure physiological parameters (pressure, flow and temperature) in the heart and in the coronary and peripheral blood vessels.

This last generation coronary guidewire, with multifunctionality sensor chip on its tip, enables multiple parameters assessment with one wire. It allows FFR assessment through pressure measurements and Coronary Flow Reserve (CFR) and IMR assessment through temperature and pressure measurements.

These indexes allow the functional evaluation of coronary stenosis and the PCI optimization.

IMR is a diagnostic and reproducible index to quantitatively evaluate the microcirculatory pathology and is calculated dividing myocardial pressure drop by the flow.

Measuring the index in revascularized myocardial area and considering as null the effect of collateral flow, IMR is calculated through the following simplified formula :

$$IMR = P_d \cdot T_{mn}$$

*(with the maximal hyperemia condition)*

PressureWire Certus is a Class III marked release guidewire. As for all the traditional guidewire, it is not intended to be left in the human body. It is contraindicated for the use in the cerebrovascular system.

## 2.6 Study Size and Duration

The total sample size is calculated in 242 patients to be enrolled by participant centers following the protocol indication.

First enrollment has been done in June 2013.

Enrollment period will be approximately 30 months.

Patients will participate in this investigation for approximately 12 months from enrollment to the last follow-up.

Study duration will be approximately 3/4 years.

The number of participant centers is foreseen as up to 20.

### 3 Protocol Description

#### 3.1 Overview

The following table lists study activities that are performed at each scheduled visit.

Table 2: Activities performed at each scheduled visit

Visit	When	Type	Activities
Enrollment & Procedures & Predischarge	In Hospital Visits	In-Clinic	
 
▪ Patient Eligibility
 
▪ Patient Informed Consent
 
▪ Patient Demographics
 
▪ Patient Physical Examination
 
▪ Patient Cardiovascular History
 
▪ Patient Medical History
 
▪ Risk and Functional Classifications
 
▪ Patient Current Cardiac Medications
 
▪ Cholesterol/Triglycerides/Enzymes+
 
▪ Echocardiography
 
▪ 12-Lead ECG
 
▪ Procedure data
 
▪ Discharge evaluation
 
▪ Adverse Events *
 

1M Follow Up	$30 \pm 7$ days post-primary PCI	In-Clinic	
 
▪ Patient clinical status and medication
 
▪ Cholesterol/Triglycerides/Enzymes+
 
▪ NYHA & CCS class assessment
 
▪ Adverse Events *
 

6M Telephone Follow Up	$183 \pm 14$ days post-primary PCI		
 
▪ Patient clinical status and medication
 
▪ NYHA & CCS class assessment
 
▪ Adverse Events *
 

12M Follow Up	$365 \pm 14$ days post-primary PCI	In-Clinic	
 
▪ Patient clinical status and medication
 
▪ Cholesterol/Triglycerides/Enzymes+
 
▪ NYHA & CCS class assessment
 
▪ Echocardiography
 
▪ Adverse Events *
 

\*: If applicable

+: refer to table 1 for timing and details

